3.3 Withdrawal Criteria

1) Withdrawal decided by the investigator

Withdrawal from the study decided by the investigator means that a subject withdraws from the study when the investigator decides such subject is unsuitable to continue the study due to the following situations during the study, including but not limited to:

- The subject has some comorbidities, complications or deterioration of the condition during the clinical study, and is not suitable to continue the study; or any AEs or clinically significant laboratory abnormality, and is considered as not appropriate to continue participating in the study by the investigator.
- Major protocol deviation. After randomization, the subject dose not meet the inclusion criteria of the study protocol, or does not follow the requirements of the study protocol, and is judged by the investigator that continuing to participate in the study may cause unacceptable risks to the health of the subject.
- The subject does not comply with the treatment regimen of investigational drug and the study follow-up procedures as judged by the investigator (e.g., non-compliance with the medical order in terms of route of administration, study visits, etc.).
- Continued treatment is considered by the investigator to be detrimental to the subject (e.g., pregnancy).
- Withdrawal due to hypoglycemia (see Section 3.3.1 in the protocol).
- Inability to receive hyperglycemia salvage therapy (e.g., subject has a contraindication to the salvage therapy).

• Failure in hyperglycemia salvage therapy (see Section 3.3.2 in the protocol).

• Other conditions considered as not suitable for further participation in this study by the investigator. (Note: The specific reason should be recorded in "Specific Description" of the electronic case report form (eCRF)).

Protocol No.: HTD1801.PCT103

2) Subject's voluntary withdrawal from the study

According to ICFs, if the subject is unwilling to continue participating in clinical study, he/she has the right to withdraw from the study at any time of the study. The subject who withdraws from the study during the screening phase is defined as "screening failure"; the subject who withdraws from the study during the introduction period/before randomization is defined as "randomization failure". During the double-blind treatment phase after randomization, if the subject dose not continue receiving medication and tests therefore is lost to follow-up although he/she does not explicitly propose to withdraw from the study, this subject is also defined as "withdrawal" (or "dropout"). The investigator should learn and record the reasons for withdrawal as much as possible, e.g., the subject consciously feels intolerable to certain adverse reactions, cannot to continue to participate in clinical studies for other reasons, or is lost to follow-up without explaining the reason, etc.

To ensure subject safety, specific criteria for withdrawal from study treatment due to hypoglycemia and failure in hyperglycemia salvage therapy are described in Sections 3.3.1 and 3.3.2.

3) Disposal for subject withdrawal

Investigators must fill in the reason for withdrawal in the eCRF and contact subjects where possible. Subjects who withdraw from the study should return the subject dairy, any remaining investigational drug and packaging of the used investigational drug.

For subjects who fail to be randomized and withdraw early without using the investigational drug after randomization, the safety follow-up visit at 4 weeks after the last dose during the introduction period is not mandatory in this study; if the subjects have AEs at withdrawal, they should be followed up until the events are resolved, unless the subjects are "lost to follow-up" or the events cannot be resolved because of their disease as judged by the investigator.

For subjects who have received at least one investigational drug and withdraw from the study early after randomization, the last dose time should be recorded if possible, and the subjects are recommended to return to the study site for all tests at withdrawal follow-up visit within 1 week of confirmed withdrawal, and to receive the safety follow-up visit at 4 weeks after the last dose. The subjects who withdraw from the study should be followed up until all existing AEs and SAEs are resolved; after subjects discontinue the study treatment, investigators should follow up and report all new AEs and SAEs occurred within 4 weeks after the last dose until the above-mentioned AEs are resolved, unless the subjects are "lost to follow-up" or the events cannot be resolved because of their disease at the investigator' discretion.

Subjects who withdraw from the study early will not be substituted.

Note: "Lost to follow-up" refers to failure to contact the subject by a minimum of 3 times (each on a different calendar day) with documented method (such as by telephone or email). All attempts should be recorded.

3.3.1 Principles for withdrawal due to hypoglycemia

3.3.1.1 Definition of hypoglycemia

In this study, hypoglycemia is divided into the following categories according to the severity based on the Guidelines for the Prevention and Treatment of Type 2 Diabetes Mellitus in China (2020):

Grade 1 hypoglycemia: blood glucose \leq 3.9 mmol/L and \geq 3.0 mmol/L.

Grade 2 hypoglycemia: blood glucose <3.0 mmol/L.

Grade 3 hypoglycemia: Serious event requiring help from others, with altered consciousness and/or physical changes, but no specific blood glucose threshold.

Protocol No.: HTD1801.PCT103

If the subject has the symptoms of hypoglycemia, but is not tested for the blood glucose or has the fingertip or venous blood glucose >3.9 mmol/L, then the subject should not be recorded. The following symptoms may be attributed to hypoglycemia: tremors, hot flashes, dizziness, anxiety, dizziness, palpitations, and hazy vision.

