3.3.1.2 Principles for withdrawal due to hypoglycemia

If the subject experiences 1 Grade 3 hypoglycemia during the double-blind treatment phase, and there are no other major causes for hypoglycemia (for example, increased physical activity or missed meals, etc.) other than the investigational drug, then the investigational drug should be discontinued, and the subject will withdraw from this study. The cause for withdrawal should be recorded as "withdrawal due to hypoglycemia", and other anti-diabetic drug treatment will be given by the investigator in accordance with clinical practice.

If the subject experiences 2 < Grade 3 hypoglycemia during the double-blind treatment phase, and there are no other major causes for hypoglycemia (for example, increased physical activity or missed meals, etc.) other than the investigational drug, then the investigational drug should be discontinued, and the subject will withdraw from this study. The cause for withdrawal should be recorded as "withdrawal due to hypoglycemia", and other anti-diabetic drug treatment will be given by the investigator in accordance with clinical practice and in compliance with the requirements of the protocol.

If the subject experiences 1 Grade 3 hypoglycemia during the salvage therapy (see Section 5.1.3.3), and there are no other major causes for hypoglycemia (for example, increased physical activity or missed meals, etc.) other than the investigational drug and the salvage therapy drug, then the investigational drug and the salvage therapy drug should be discontinued, and the subject will withdraw from this study. The cause for withdrawal should be recorded as "withdrawal due to hypoglycemia", and other anti-diabetic drug treatment will be given by the investigator in accordance with clinical practice and in accordance with the requirements of the protocol.

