If the subject experiences 2 < Grade 3 hypoglycemia during the salvage therapy, and there are no other major causes for hypoglycemia (for example, increased physical activity or missed meals, etc.) other than the investigational drug and the salvage therapy drug, then the salvage therapy drug should be discontinued, and the subject will continue to receiving the investigational drug; if the subject has another one hypoglycemia event (Grade 1 or 2 or 3) thereafter, and there are no other major causes for hypoglycemia (for example, increased physical activity or missed meals, etc.) other than the investigational drug, then the investigational drug should be discontinued, and the subject will withdraw from this study. The cause for withdrawal should be recorded as "withdrawal due to hypoglycemia", and other anti-diabetic drug treatment will be given by the investigator in accordance with clinical practice and in accordance with the requirements of the protocol. If the subject has blood glucose level above the hyperglycemia threshold specified in the protocol again after withdrawal of the salvage therapy due to the above hypoglycemia, the investigator can judge whether to start the salvage therapy again or allow the subject to directly withdraw from the study according to the actual conditions.

Subjects should be informed of contacting the study site during self-monitoring in case of:

1) Any episode of hypoglycemia requiring help from others (i.e., Grade 3 hypoglycemia);

2) Any episode of hypoglycemia with fingertip blood glucose <3.9 mmol/L, with or without symptoms.

Protocol No.: HTD1801.PCT103

Note: As described above, subjects will record symptoms and/or fingertip blood glucose measurements they believe to be related to hypoglycemia in the subject diary. Investigators should check the hypoglycemia records in the subject diary, evaluate each episode of hypoglycemia, and carefully inquire about the presence of symptoms during hypoglycemia episode, management, and duration at episode of hypoglycemia. All episodes of hypoglycemia that are judged and confirmed by the investigator must be recorded in the Hypoglycemia Assessment Form of the eCRF.

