8.1.2 Hypoglycemia event

The date and time of onset and end of each hypoglycemia event, the classification of hypoglycemia (for the definition of hypoglycemia, see Section 3.3.1.1), blood glucose value and/or description of symptoms, measures taken and description, the determination that whether it is severe hypoglycemia and whether it is resolved, cause and description, the correlation judgment with the investigational drug and the correlation judgment with the salvage therapy drug, etc. should be recorded in detail.

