10.4.5 Safety data analysis

Based on the SS, the safety analysis is performed based on the therapy strategy.

AEs

All AEs are coded by MedDR SOC and PT. The number and percentage of AEs, such as AEs, drug-related AEs, SAEs, and other major medical events, are calculated separately, and a detailed list is provided. The incidence is calculated with the number of subjects in SS in each group as the denominator, and the chi-square test is used (Fisher's exact probability method is used based on the data) for inter-group comparison if necessary.

Hypoglycemia event

The number of subjects, percentage and number of cases of hypoglycemia events (Grade 1 hypoglycemia event, Grade 2 hypoglycemia event, Grade 3 hypoglycemia event, etc.) are analyzed.

Clinical laboratory tests

Including hematology, blood biochemistry, urinalysis and coagulation tests.

The visit results of each laboratory test and their changes from baseline are described with mean, standard deviation, median, minimum and maximum.

Protocol No.: HTD1801.PCT103

The clinical judgment results (normal, abnormal with no clinical significance, abnormal with clinical significance, and not tested) of the laboratory results before and after treatment are presented in cross tabulation.

For subjects with abnormal laboratory results during the double-blind treatment phase, the results of each examination and judgment are listed according to the abnormality with clinical significance and the abnormality without clinical significance.

Evaluation on vital signs

The results of vital signs in each visit each and their changes from baseline are described with mean, standard deviation, median, minimum and maximum.

Evaluation on physical examination

The physical examination results of each visit are described, the number of normal and abnormal subjects and percentages are calculated, and abnormal values are listed.

Evaluation on ECG

Refer to the evaluation of laboratory test indicators.

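### Section 3.3.1.1 defines Grade 3 hypoglycemia without a glucose threshold, then bars recording of symptomatic episodes that are untested or read above 3.9 mmol/L, with no exception for Grade 3

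*Protocol*

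**What the plan says.** Protocol section 3.3.1.1 sets three grades. Grades 1 and 2 are glucose ranges. Grade 3 is not: "Grade 3 hypoglycemia: Serious event requiring help from others, with altered consciousness and/or physical changes, but no specific blood glucose threshold".

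The same section then gives a recording rule. Of a symptomatic subject it says: "is not tested for the blood glucose or has the fingertip or venous blood glucose >3.9 mmol/L, then the subject should not be recorded". Immediately after it comes: "The following symptoms may be attributed to hypoglycemia: tremors, hot flashes, dizziness, anxiety, dizziness, palpitations, and hazy vision".

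Three other places bear on recording and use:

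- **Section 3.3.1.2** tells subjects to contact the site for any episode needing help from others, with no glucose condition. It adds: "All episodes of hypoglycemia that are judged and confirmed by the investigator must be recorded in the Hypoglycemia Assessment Form of the eCRF". It also attaches discontinuation and withdrawal to a single event, in the paragraph that begins "If the subject experiences 1 Grade 3 hypoglycemia during the double-blind treatment phase", provided there is no other major cause.
- **Section 8.1.2** lists what is recorded for each event, including "blood glucose value and/or description of symptoms".
- **Section 10.4.5** reports "The number of subjects, percentage and number of cases of hypoglycemia events", broken down by Grades 1, 2 and 3.

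**The concern.** The no-record sentence has two limbs: no test, or a reading above 3.9 mmol/L. Either can apply to an episode that meets the Grade 3 definition a few lines earlier, and the sentence does not exclude such episodes. It also does not say when the reading must have been taken, so a value obtained after recovery counts.

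Section 3.3.1.1 is the definition cited for the hypoglycemia safety indicator (section 7.3), for event classification (section 8.1.2) and for exclusion criterion 4. The withdrawal rules and the reported counts use the same grades. If sites differ on whether an untested severe episode is recorded, the Grade 3 count depends on the site's reading of the text as well as on what happened to the subject. A statistical analysis plan cannot repair this, because it cannot recover records that sites were told not to make.

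**Working it through.** This is a question of wording, and the plan states no figure to reproduce. The check is to take each kind of episode needing help from others, with altered consciousness and/or physical changes, and read the sections against it.

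| Glucose information | Grade 3 by definition (3.3.1.1)? | No-record sentence (3.3.1.1) | Form, if investigator confirms (3.3.1.2) | Event data (8.1.2) |
|---|---|---|---|---|
| Reading ≤3.9 mmol/L | Yes | Does not apply | Record | Value and/or symptoms |
| No reading | Yes | Do not record | Record | Symptoms suffice |
| Only reading >3.9 mmol/L | Yes | Do not record | Record | Value and/or symptoms |

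The first row is consistent. The second and third rows carry opposite instructions. The conflict inside section 3.3.1.1 needs no further assumption. The conflict with section 3.3.1.2 arises when an investigator confirms the episode on the Grade 3 definition, which asks for no glucose value.

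**Can the second and third rows occur under this protocol?** Yes, on its own procedures. For a subject with impaired consciousness, Appendix 11 puts glucose or glucagon first and repeated glucose measurement afterwards, and it provides for values above 3.9 mmol/L. The only reading may therefore be post-treatment. Recommended home testing in the double-blind phase is 1-2 times a week (study process, note 19). Section 7.3.6 asks for a test as soon as possible when symptoms are suspected, but the documents do not show that a subject who needs help will have one.

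**What is one event worth in the table?** Assume all 33 subjects planned per arm are in the safety set, and use exact (Clopper-Pearson) two-sided 95% limits.

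- 0/33: upper limit = 1 − 0.025^(1/33) = 10.6%.
- 1/33: estimate = 1/33 = 3.0%. The upper limit solves (1 − p)^33 + 33p(1 − p)^32 = 0.025, giving p of about 15.8%.

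This shows the scale of a single unrecorded event. It is not evidence that any event will be lost.

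**The case against.** The strongest reply is that the sentence was meant only for unconfirmed mild symptoms. The symptoms listed after it are mild, neither altered consciousness nor need for help is among them, and 3.9 mmol/L is the upper bound of Grade 1. That is a plausible intention and may well be the right one. The text does not state it, however, and a list of symptoms that may be attributed to hypoglycemia does not limit the rule's scope.

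A second reply is that section 3.3.1.2 requires recording only of episodes the investigator has confirmed, which is compatible with leaving unconfirmed symptoms out. This stands for Grades 1 and 2. It does not resolve a confirmed Grade 3 episode without a qualifying reading.

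A third reply concerns consequences, and it largely stands. A reader might infer that such events never reach the investigator, or vanish from the safety analysis. The documents do not support that:

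- Subjects are told to contact the site for any episode needing help.
- Investigators review diary symptoms and evaluate each episode (section 3.3.1.2).
- Section 8.1.2 foresees a record based on symptoms.
- Section 8.6.1 has all AEs entered on the eCRF, as SAEs where the criteria are met, and section 10.4.5 tabulates both.

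What remains exposed is the hypoglycemia-by-grade summary and the consistency of the Grade 3 withdrawal rule.

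**Conclusion.** The contradiction within section 3.3.1.1 is real and is one of stated rules. It also conflicts with sections 3.3.1.2 and 8.1.2. Sites that follow the no-record sentence literally would leave some Grade 3 episodes off the Hypoglycemia Assessment Form: those never tested, and those with only a reading above 3.9 mmol/L. The Grade 3 counts of section 10.4.5 could then be understated and the withdrawal rule of section 3.3.1.2 applied unevenly.

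The size cannot be estimated, because the protocol gives no expected rate of Grade 3 events and no rate of missing readings. A reader might go on to infer that the rule would remove a severe-hypoglycemia signal altogether, and nothing in the documents supports that. The most that can be said is that in arms of 33 each severe event is visible in the table. The conclusion rests on the literal wording, not on any view of how often sites would apply it. The HbA1c primary endpoint definition and the sample size calculation are not affected.

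**What to change.** Reconcile sections 3.3.1.1, 3.3.1.2 (contact, recording and withdrawal paragraphs) and 8.1.2. For recording, limit the no-record sentence in section 3.3.1.1 to episodes that do not meet the protocol's own Grade 3 definition. Episodes that do meet it are then entered on the Hypoglycemia Assessment Form with or without a glucose value, and flagged where there is none. Carry the same wording into the eCRF guidance.

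Because a Grade 3 classification feeds the withdrawal rule, the sponsor should check that the withdrawal paragraphs agree with the clarified wording. This review takes no position on the clinical rule itself.

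The cost is one clarifying sentence and a line of eCRF guidance. The downside is a few Grade 3 records without a confirming glucose value. The flag lets these be listed separately or examined with and without.

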3.3.1.2 Principles for withdrawal due to hypoglycemia

If the subject experiences 1 Grade 3 hypoglycemia during the double-blind treatment phase, and there are no other major causes for hypoglycemia (for example, increased physical activity or missed meals, etc.) other than the investigational drug, then the investigational drug should be discontinued, and the subject will withdraw from this study. The cause for withdrawal should be recorded as "withdrawal due to hypoglycemia", and other anti-diabetic drug treatment will be given by the investigator in accordance with clinical practice.

If the subject experiences 2 < Grade 3 hypoglycemia during the double-blind treatment phase, and there are no other major causes for hypoglycemia (for example, increased physical activity or missed meals, etc.) other than the investigational drug, then the investigational drug should be discontinued, and the subject will withdraw from this study. The cause for withdrawal should be recorded as "withdrawal due to hypoglycemia", and other anti-diabetic drug treatment will be given by the investigator in accordance with clinical practice and in compliance with the requirements of the protocol.

If the subject experiences 1 Grade 3 hypoglycemia during the salvage therapy (see Section 5.1.3.3), and there are no other major causes for hypoglycemia (for example, increased physical activity or missed meals, etc.) other than the investigational drug and the salvage therapy drug, then the investigational drug and the salvage therapy drug should be discontinued, and the subject will withdraw from this study. The cause for withdrawal should be recorded as "withdrawal due to hypoglycemia", and other anti-diabetic drug treatment will be given by the investigator in accordance with clinical practice and in accordance with the requirements of the protocol.

If the subject experiences 2 < Grade 3 hypoglycemia during the salvage therapy, and there are no other major causes for hypoglycemia (for example, increased physical activity or missed meals, etc.) other than the investigational drug and the salvage therapy drug, then the salvage therapy drug should be discontinued, and the subject will continue to receiving the investigational drug; if the subject has another one hypoglycemia event (Grade 1 or 2 or 3) thereafter, and there are no other major causes for hypoglycemia (for example, increased physical activity or missed meals, etc.) other than the investigational drug, then the investigational drug should be discontinued, and the subject will withdraw from this study. The cause for withdrawal should be recorded as "withdrawal due to hypoglycemia", and other anti-diabetic drug treatment will be given by the investigator in accordance with clinical practice and in accordance with the requirements of the protocol. If the subject has blood glucose level above the hyperglycemia threshold specified in the protocol again after withdrawal of the salvage therapy due to the above hypoglycemia, the investigator can judge whether to start the salvage therapy again or allow the subject to directly withdraw from the study according to the actual conditions.

Subjects should be informed of contacting the study site during self-monitoring in case of:

1) Any episode of hypoglycemia requiring help from others (i.e., Grade 3 hypoglycemia);

2) Any episode of hypoglycemia with fingertip blood glucose <3.9 mmol/L, with or without symptoms.

Protocol No.: HTD1801.PCT103

Note: As described above, subjects will record symptoms and/or fingertip blood glucose measurements they believe to be related to hypoglycemia in the subject diary. Investigators should check the hypoglycemia records in the subject diary, evaluate each episode of hypoglycemia, and carefully inquire about the presence of symptoms during hypoglycemia episode, management, and duration at episode of hypoglycemia. All episodes of hypoglycemia that are judged and confirmed by the investigator must be recorded in the Hypoglycemia Assessment Form of the eCRF.

